5.5.4.4. Medical intervention

Vaccine efficacy will be summarized with a 95% confidence interval (methods in Appendix 8)

When sufficient number of events are observed, an adjusted confidence interval will be calculated with the alpha-level α^* derived as detailed in section 2. To evaluate the hypothesis $H_0: VE \leq 0\%$, the lower-limit of the adjusted confidence interval will be compared to 0%, the hypothesis of protection on medical intervention endpoints will be rejected if the lower limit of the confidence interval is $> 0\%$.

For cases, the follow-up time is defined as the time between double-blind vaccination and the onset of the first event (according to the considered event linked to the medical intervention). For non-cases, it is the time between double-blind vaccination and data base cut off date (for subjects ongoing) or study discontinuation.

The reason linked to medical intervention will be tabulated.

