4. POPULATIONS (ANALYSIS SETS) FOR ANALYSIS

Vaccine assignment will be analyzed according to an as-treated principle. The analysis sets that are used for the various analyses are described in [Table 5](#).

Table 5 Analysis Sets

Analysis Sets	Description
Enrolled	The enrolled analysis set includes all participants who signed the ICF and who were not screen failures
Randomized	The randomized analysis set includes all participants who were randomized in the study.
Full Analysis Set (FAS)	All randomized participants with a documented study vaccine administration, regardless of the occurrence of protocol deviations and serostatus at enrollment.
Per Protocol Efficacy Set (PP; primary efficacy analysis set for vaccination studies)	Participants in the FAS who received double-blind study vaccine and who were seronegative at the time of double-blind vaccination and who have no major protocol deviations that were judged to possibly impact the efficacy of the vaccine. Participants who became aware of their study vaccine allocation will cease to be part of the PP population. See below for a definition.
Per Protocol Immunogenicity Analysis Set (PPI)	All randomized and vaccinated participants, including those who are part of the Immuno Subset and for whom immunogenicity data are available, excluding participants with major protocol deviations expected to impact the immunogenicity outcomes. In addition, for participants who experience a SARS-CoV-2 event (molecularly confirmed), samples taken after the event and samples taken outside protocol windows will not be taken into account in the assessment of the immunogenicity. The PPI population is the primary immunogenicity population. For key tables, sensitivity immunogenicity analyses will also be performed on the FAS, including participants who are part of the Immuno Subset for whom immunogenicity measures are available. Excluded samples might be taken into account as well in the sensitivity analysis. Analyses of vaccine immunogenicity and immune correlates of risk will be based on PPI.

For the PP the following additional criteria will be applied:

- having received the double-blind vaccine according to the randomization schedule
- having received at least 80% of the scheduled double-blind vaccination volume (according to the administration log)
- met inclusion criteria 1 (informed consent was obtained)

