5. STATISTICAL ANALYSES

5.1. General Considerations

Unless otherwise indicated, all analyses will pool data across ages and with/without co-morbidities for evaluation without stratification.

Analysis adjusting for randomization factors will be explicitly mentioned when done and will include the age groups and with/without co-morbidities only.

Stratification for (mobile) site unit at the time of randomization was done to ensure balance in exposure to SARS-CoV-2 between randomized groups over time because of the spatiotemporal evolution of the epidemic. However, including all stratification factors (age by comorbidity by (mobile) site) in the analysis will result in a large number of ‘empty strata’ (i.e. without cases) as the TNE of 154 is substantially lower than the anticipated number of stratification levels. Therefore no summaries will be provided by this stratification factor (mobile unit).

The final analysis planned at the end of the double blind phase, comparing vaccine versus placebo, will include efficacy and safety data collected during the ‘double blind phase’ of the trial, i.e. with an onset date of the event (or censor date) up to unblinding date.

To include the available data after unblinding, this analysis – comparing vaccine versus placebo – will be supplemented for primary and secondary endpoints with an analysis evaluating all available events until study discontinuation or upon administration of another authorized/approved vaccine up to the data lock point. Events that occurred after cross-over to another COVID-19 vaccine (including the Janssen Vaccine if received outside of the study) will be tabulated separately.

The analysis of the open-label phase (comparing efficacy between immediate vaccination versus delayed vaccination with the Janssen COVID-19 vaccine during the open-label phase of the study will include efficacy and safety data after unblinding and will be described in a separate SAP. Per protocol amendment 5, this analysis is planned when all subjects had at least one year of follow-up.

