5.1.4. Unblinding due to cross-over for Janssen Vaccine

Section 6.4 from CTPA4 details the procedures to unblind participants at their Month6/Unblinding visit and offer participants who received placebo a single dose of Ad26.COV2.S vaccine. For all participants that are still in the study and did not have had a COVID-19 infection, nor have been censored, the Month6/Unblinding visit will mark the date of censoring for the double blind phase.

If participants decide to continue the study at the Month6/Unblinding visit, participants will be continued to be followed up and data will be collected and be analyzed separately.

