5.4.5. Supportive analyses

The primary analysis will be supplemented with the following analyses.

For subjects with molecularly confirmed COVID-19, the follow-up time is defined as the time between double-blind vaccination and the time of onset of the case. For all subjects without COVID-19, follow-up time is defined as the time since vaccination until the date of unblinding or study discontinuation.

Time to first occurrence of molecularly confirmed moderate or severe/critically ill COVID-19 is defined as the time between double-blind vaccination until onset of the case for the PP set. Subjects without moderate and severe/critically ill COVID-19 are censored at their follow-up time as defined above.

In a supportive analysis of the primary efficacy endpoint, vaccine efficacy will be estimated with an associated two-sided confidence interval (Wald test) based on the hazard ratio obtained from a Cox proportional hazards regression model. The analysis will be stratified for age (≥ 60 yrs, < 60 yrs) and comorbidities (with or without comorbidities). The strata will be based on the values in the database (which may differ to the strata as recorded in IWRS). The alpha-level at the time of crossing the boundary will be used to calculate the confidence interval.

As a supplementary analysis, a Negative Binomial model (using an asymptotic model including estimation of a dispersion parameter) will also be fitted.

The primary and supportive analysis as described for moderate and severe/critically ill COVID-19 cases in the per-protocol population in seronegative subjects will be repeated using the following analysis populations and endpoints:

- FAS, SN (seronegative) with onset of molecularly confirmed, moderate and severe/critically ill COVID-19 one day after double-blind vaccination
- PP, SN subjects with onset of molecularly confirmed, moderate and severe/critically ill COVID-19, at least 28 days after double-blind vaccination, thereby excluding subjects who were seropositive at or before Day 29 based on PCR or serological testing of Day 29 (subjects with missing data will be included)
- PP, SN subjects with onset of molecularly confirmed, moderate and severe/critically ill COVID-19, at least 14 and at least 28 days after double-blind vaccination, thereby excluding subjects with a missing result for the baseline serology sample

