5.4.7. Tabulations and Graphical displays

The time to onset of the first occurrence of molecularly confirmed COVID-19 (definition in section 5.2.4) will be graphically summarized using Kaplan-Meier methods for the following subgroups:

For moderate or severe/critical COVID-19,

- PP, seronegative subjects only with onset at least 14 days and at least 28 days after double-blind vaccination (co-primary endpoints)
- PP, seronegative subjects only with onset 1 day after double-blind vaccination
- PP, seronegative and seropositive subjects with onset 1 day after double-blind vaccination
- FAS, seronegative subjects only with onset 1 day after double-blind vaccination
- FAS, seronegative and seropositive subjects with onset 1 day after double-blind vaccination

*Note that in the PP there are no baseline-seropositive subjects – this population is defined as subjects who are baseline-seropositive and otherwise comply with the PP analysis set definition (e.g. no major protocol deviations).

These graphs will be summarized combined as well as for each type of infection separately (moderate or severe/critically ill COVID-19).

Furthermore, the number of events and incidence for each endpoint and population (#of events/#person-years of follow-up) will be tabulated by randomized group. For the tabulations regardless of serostatus, cases will be additionally summarized by serostatus at baseline and combined.

To assess potential time-effects of VE, two additional graphical explorations will be conducted. First, the Kaplan-Meier method will be used to plot the estimated cumulative incidence rates over time for the vaccine and placebo groups. This method will be used to estimate cumulative VE over time, defined as $[(1 \text{ minus ratio (vaccine/placebo)} \text{ of cumulative incidence by time } t) \times 100\%]$ with the method of Parzen, Wei and Ying applied to estimate pointwise and simultaneous $(1 - \alpha) \times 100\%$ CIs. Secondly, the method of Gilbert et al. (2002) will be used to evaluate VE over time based on the ratio of the smoothed instantaneous hazard in the vaccine and the placebo arm. More specifically, graphs will be created with $[(1 \text{ minus ratio (vaccine/placebo)} \text{ of smoothed instantaneous hazard by time } t) \times 100\%]$ and accompanying pointwise and simultaneous $(1 - \alpha) \times 100\%$ CIs over time since vaccination.

Any subgroup analysis for VE will also be visualized with forest plots.

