5.5. Secondary Endpoint(s) Analysis

5.5.1. Tabulations and graphical displays

The time to onset of the first occurrence of molecularly confirmed COVID-19 will be graphically summarized using Kaplan-Meier methods for the following analysis populations following subgroups:

- PP, seronegative subjects only with onset at least 14 days and at least 28 days after double-blind vaccination
- PP, seronegative subjects only with onset 1 day after double-blind vaccination
- PP, seronegative and seropositive subjects with onset 1 day after double-blind vaccination
- FAS, seronegative subjects only with onset 1 day after double-blind vaccination
-

*Note that in the PP there are no baseline-seropositive subjects – this population is defined as subjects who are baseline-seropositive and otherwise comply with the PP analysis set definition (e.g. no major protocol deviations).

These graphs will be prepared regardless of severity according to the case definitions mild, moderate and severe and for the US FDA harmonized case definition. Furthermore, the graph will be prepared by severity (for mild COVID-19 only, COVID-19 requiring medical intervention).

The number of events and event rate for each endpoint and population (#of events/#person-years of follow-up) will be tabulated by randomized group.

Unless otherwise indicated, follow-up time for each subject is defined as time since double-blind vaccination until onset of a COVID-19 episode or the date of unblinding (For subjects without a COVID-19 episode in the double blind phase).

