Severe/critical infection	A subject is considered as an event when the first occurrence of molecularly confirmed COVID-19 case meeting severe/critical definition with onset at least 14 days and at least 28 days post double-blind vaccination.
COVID-19 requiring Medical intervention	
COVID-19 events requiring medical intervention including hospitalization based on objective findings such as ICU admission, mechanical ventilation, ECMO, decreased oxygenation, X-ray, CT findings, use of supportive medications or clinical course following adjudication by the CSAC with onset at least 14 days and at least 28 days post double-blind vaccination
 
The evaluation whether the endpoint is linked to objective measures will be done through the adjudication committee using all available information.
 
In addition, an algorithmic interpretation will be done, based on the MRU questionnaire only for consistency with the primary analysis.

The confirmatory estimands therefore are

Population: Prior SARS-CoV-2-uninfected, adults ≥ 18 years with or without comorbidities for COVID-19

Endpoint: as defined above.

Interventions: Ad26.COV2.S 5×10^{10} virus particles and placebo

Summary Measure: Vaccine Efficacy: $100 \times (1 - \text{ratio of endpoint mean vaccine/placebo})\%$

Intercurrent Events: /

Data handling for estimator: Subjects with major protocol deviations potentially impacting efficacy will be excluded from the analysis. Subjects with a positive serology test at baseline will be excluded from the analysis.

For the secondary endpoints all available cases at the time of data base cut off will be included in the analysis according to the pre-specified analysis population and time window for endpoint calculation.

The populations for analysis for the secondary endpoints are presented in [Table 8](#).

Table 8 Key confirmatory secondary endpoints and analysis set evaluations

	Key analysis population for evaluation of the statistical hypothesis	Supportive analysis set
Any symptomatic infection (BOD)	Per-Protocol analysis set baseline-Sero-Negative subjects with onset of infection at least 14 days and at least 28 days post double-blind vaccination	PP, SN/SP, Day 28* FAS, SN, Day 1 FAS, SN/SP, Day 1*
Any SARS-CoV-2 infection	Per-Protocol analysis set Sero-Negative subjects with onset of infection at least 28 day post double-blind vaccination	FAS, SN, Day 1 FAS, SN/SP, Day 1* PP, SN/SP, Day 28

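### Section 5.5.4.4 runs medical-intervention follow-up past unblinding to the database cut-off, against the plan's own double-blind censoring rule, so the rate in both arms is understated

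*SAP*

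**What the plan says.** Section 5.5.4.4 sits under the heading for double-blind analysis methods. It states: "For non-cases, it is the time between double-blind vaccination and data base cut off date (for subjects ongoing) or study discontinuation". Unblinding is not mentioned. The Introduction gives the cut-off as 9JUL2021.

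The rest of the SAP ends double-blind follow-up earlier:

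- Section 5.1 limits the double-blind analysis to data "with an onset date of the event (or censor date) up to unblinding date"; Section 5.1.5 repeats this scope.
- Section 5.1.4, for participants still under follow-up and without infection: "the Month6/Unblinding visit will mark the date of censoring for the double blind phase".
- Section 4: "Participants who became aware of their study vaccine allocation will cease to be part of the PP population". The per-protocol (PP) set is the key set for this endpoint in Table 8.
- Section 5.4.5, primary endpoint: "For all subjects without COVID-19, follow-up time is defined as the time since vaccination until the date of unblinding or study discontinuation".
- Section 5.5.1, secondary endpoints: "follow-up time for each subject is defined as time since double-blind vaccination until onset of a COVID-19 episode or the date of unblinding". This default gives way wherever another rule is indicated.

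Person-time is used twice. Section 5.5.1 tabulates events over person-years by randomized group, and Appendix 8 estimates VE as 1 − r·n2/n1, where r = N1/N2 is the ratio of follow-up times (placebo over vaccine).

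**The concern.** The Section 5.5.1 default yields to any specific rule, so Section 5.5.4.4 is an operative exception and not merely loose wording. A programmer following it would keep accruing person-time after participants know their allocation, and after placebo recipients have received active vaccine. Sections 4, 5.1 and 5.1.4 bar events from that same period. The denominator therefore covers time that the numerator does not.

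At stake is the reported incidence of a confirmatory secondary endpoint, on a person-time base that differs from the one set for the primary endpoint and, by default, for the other secondary endpoints. Two programmers working from different sections could report rates about twofold apart.

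**Working it through.** **Inputs from the SAP.** Cut-off 9 Jul 2021 (Introduction). Study start 21 Sep 2020 (Section 5.4.8). Median double-blind follow-up at the final analysis about 112 days (Section 5.4.3). Allocation 1:1. VE = 1 − r·n2/n1 (Appendix 8). 23 events, the number deemed sufficient for this endpoint (Section 3.5.2).

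**Assumptions.** Vaccination dates after study start, 20,000 participants per arm, the case split, and any imbalance in double-blind time between arms. The 112-day median is applied to every participant.

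**The plan's own figures.** The SAP states no person-time for this endpoint, so there is none to reproduce. The conditional binomial approach behind Appendix 8 was checked on the primary endpoint: it returns the target of 154 events, power of 86.22% and type I error of 2.398%, as stated.

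**Step 1: effect on the rate.** Understatement factor = days from vaccination to cut-off ÷ 112.

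| Vaccination date | Days to cut-off | Factor | Rate too low by (1 − 112/days) |
|---|---|---|---|
| 21 Sep 2020 (study start) | 291 | 2.60 | 62% |
| 15 Nov 2020 (assumed) | 236 | 2.11 | 53% |
| 15 Dec 2020 (assumed) | 206 | 1.84 | 46% |
| 31 Jan 2021 (assumed) | 159 | 1.42 | 30% |

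Example with 19 placebo and 4 vaccine cases, 20,000 per arm, in cases per 1,000 person-years:

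- To unblinding (112 days): placebo 19 ÷ (20,000 × 112/365.25) × 1,000 = 3.10; vaccine 0.65.
- To cut-off (236 days): placebo 1.47; vaccine 0.31.

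**Step 2: effect on VE.**

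- Time balanced between arms: r = 1 under either rule, and VE = 1 − 4/19 = 78.9% both ways.
- Placebo double-blind time 10 days shorter: r = 102/112 = 0.911, VE to unblinding = 1 − 0.911 × 4/19 = 80.8%.
- Placebo double-blind time 10 days longer: r = 122/112 = 1.089, VE to unblinding = 77.1%.
- As written, with equal time to cut-off in the two arms: 78.9% in every case.

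The difference is about 2 points in either direction.

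**The case against.** **Leftover text.** Before systematic unblinding, the cut-off was largely the right end of follow-up, and the sentence may survive from the primary analysis. The Introduction says that parts no longer applicable are shown in grey. If the formatted SAP greys this sentence, the Section 5.5.1 default governs and little remains. The wording itself does not mark it as superseded, and the endpoint is still live: Section 5.5.2.1 defines it by adjudication and keeps an algorithmic version for consistency with the primary analysis. This objection stands as a reason for moderate confidence only.

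**The PP rule already cuts the time.** One can argue that loss of PP membership at unblinding ends follow-up whatever Section 5.5.4.4 says. In that case the sentence cannot be carried out as written in the key analysis set, and it still needs correcting.

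**The size is rough.** This stands. One study-wide median is set against individual dates. Early enrollees plausibly had longer double-blind follow-up, which would shrink the upper end of the range. The SAP gives no vaccination dates.

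**Stronger readings a reader might infer.**

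- *Events after crossover count against placebo and dilute VE.* Section 5.5.2.1 includes all cases available at cut-off, but only within the prespecified population and time window. Sections 4, 5.1 and 5.1.5 exclude events after unblinding. The analysis that uses post-unblinding data counts in-study crossover time as vaccine time, and Section 5.5.5 repeats it only for severe events and the FDA definition.
- *Person-time from vaccination is also an error, because this endpoint counts events only* "with onset at least 14 days and at least 28 days post double-blind vaccination". Starting at vaccination is stated openly and used uniformly in the double-blind definitions. It nearly cancels in VE under 1:1 allocation. The different rule in Section 5.4.8 belongs to a separate calendar-time model.
- *The confirmatory result could be overturned.* With an assumed 17:6 split and placebo time 10 days longer, the 95% lower limit moves from +6.2% to −2.2%. The SAP supports neither assumption. Under Section 2, an endpoint already tested at the primary analysis is now only summarized with a 95% confidence interval; whether this one was tested is not stated.

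**Conclusion.** Section 5.5.4.4 contradicts the double-blind end of follow-up set in Sections 4, 5.1, 5.1.4, 5.1.5, 5.4.5 and 5.5.1. Followed literally, it understates the absolute medical-intervention rate in both arms. The factor of about 1.4 to 2.6 depends on the assumed vaccination date and on giving everyone the 112-day median. The error is in the rates; the documents do not show a wrong VE, since VE shifts only if double-blind person-time differs between arms and the SAP gives no data on that.

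This is a should-fix. The contradiction itself is plain. Confidence is moderate because the sentence may be superseded text.

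**What to change.** In Section 5.5.4.4, define non-case follow-up as the time from double-blind vaccination to the earliest of unblinding, receipt of another COVID-19 vaccine, study discontinuation or data cut-off. This matches the unblinding stop used for the other double-blind endpoints and the Section 4 rule that drops PP data from another SARS-CoV-2 vaccine onward. State also that a participant whose first event begins after unblinding is a non-case in this analysis, censored at unblinding.

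Footnote any tabulated rate that differs from the primary analysis for this reason. Optionally, label the Day 15 and Day 29 rates as counted from vaccination; their derivation need not change.

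The cost is a short wording change in the SAP, one derivation in the time-to-event dataset, and the footnote. No new data are needed.

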5.5.4.5. AUC viral load

To compare VL-AUC after infection between the active and placebo groups, the exact Wilcoxon Rank Sum test will be performed.

Values below the LLOQ will be imputed with 1 when detected and with 0 when not detected.

These imputations will be used when calculating the AUC based on equation (1). In addition, in case some observations are missing at the first timepoint after infection and/ or the last timepoint after challenge, missing values should be imputed with 0. No other missing values will be imputed.

AUC-VL values will be descriptively summarized (mean, median, SD, SE, range) by randomized group and COVID-19 severity (all symptomatic infections, mild, moderate to severe/critical).

Individual profiles of viral load over time and $\log_{10}[\text{viral load}]$ over time since onset of a COVID-19 episode will be summarized by randomized group and severity of COVID-19.

The vaccine efficacy against AUC-VL will be estimated through the geometric mean ratio of AUC-VL with associated 95% confidence interval.

As the comparison of the AUC VL after infection between the active and placebo groups is based on post-randomization groups, this analysis may not assess the causal effect of the vaccine on viral load. A sensitivity analysis as described by Gilbert et al. (2003) will be carried out. In this sensitivity analysis, a logistic selection bias model is employed to define a causal estimator for the vaccine effect on viral load. The unknown slope (b) of this logistic model determines the amount of selection bias; b is varied over a plausible range of values. For each value of b , a non-parametric estimate of the causal vaccine effect is calculated. A confidence interval and p-values for the appropriate hypothesis of interest are obtained by bootstrap. If $b < 0$, there is a selection bias towards a lower viral load in the vaccine group as compared to the placebo group. When $b = 0$, no selection bias is assumed. The hypothesis of interest is the one-sided hypothesis of a reduction of the viral load. Therefore, values of $b \leq 0$ will be considered (from -5 to 0 in steps of 0.01). The estimate of the causal vaccine effect with its $100*(1-2*\alpha)$ % confidence interval and the p-value for the one-sided hypothesis of a viral load reduction in the vaccine group will be plotted against the assumed value of b .

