5.5.3. Supportive Secondary Endpoint(s)

To understand and characterize the vaccine efficacy against any symptomatic infection, as well as under any infection, the following supportive endpoints will be supplemented with the confirmatory secondary endpoints.

The evaluation of secondary endpoints will be done in the per-protocol analysis set in seronegative subjects, with onset at least 14 and at least 28 days after double-blind vaccination. All analyses will be repeated regardless of serostatus.

	Endpoint definition
Mild infection	A subject is considered as an event when the first occurrence of molecularly confirmed COVID-19 case meeting mild definition with onset at least 14 and at least 28 days post double-blind vaccination.
Moderate infection	A subject is considered as an event when the first occurrence of molecularly confirmed COVID-19 case meeting moderate definition with onset at least 14 and at least 28 days post double-blind vaccination.
US FDA Harmonized COVID-19 cases	A subject is considered as an event when the first occurrence of molecularly confirmed COVID-19 case meeting the US FDA harmonized case definition with onset at least 14 and at least 28 days post double-blind vaccination
Viral Load AUC (VL-AUC)	
Area under the viral load-time curve (VL-AUC in \log_{10} copies/ml) of SARS-CoV-2 viral RNA load as determined by quantitative RT-PCR assay of nasal available samples during the COVID-19 episode.
 
Nasal swab samples are taken at the start of the COVID-19 episode and every 2 days thereafter for the next 14 days or until 2 consecutive negative swabs, whichever occurs later.
 
VL-AUC is calculated based on the viral load values until resolution of the COVID-19 episode.
 
In the calculation of the AUC, all available information (date, timing in hours, and minutes as captured in the data base will be used, but the AUC result will be reported in hours), of the assessment, is taken into account.
 
Data handling regarding the following will be added to the Data Presentation Specifications (DPS):
 
 • PCR local lab versus central lab data • saliva • handling of values below LLOQ/LLOD

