	$AUC VL = \sum_{i=2}^T \frac{[VL_{t_i} + VL_{t_{(i-1)}}]}{2} [t_i - t_{(i-1)}]$ 
where
 
t_i = (actual) timepoint i
 
t_{i-1} = (actual) timepoint $(i-1)$
 
T = last timepoint
 
t_1 = first timepoint
 
VL_{t_i} = \log_{10} viral load at (actual) timepoint i
 
$VL_{t_{(i-1)}}$ = \log_{10} viral load at (actual) timepoint $(i-1)$
 
This will be calculated for all subjects with a molecularly confirmed infection.

--	---

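### VL-AUC scores a missing first swab of a confirmed episode as undetectable virus, which lowers that participant's AUC; the arm comparison is biased only if missing first swabs differ by arm

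*SAP*

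**What the plan says.** SAP Section 5.5.3 lists VL-AUC as a supportive secondary endpoint for molecularly confirmed infections. On sampling it says "Nasal swab samples are taken at the start of the COVID-19 episode and every 2 days thereafter for the next 14 days", or until two consecutive negative swabs if that is later. On the end of the curve it says "VL-AUC is calculated based on the viral load values until resolution of the COVID-19 episode". The formula is a trapezoid whose ordinates are the log10 "viral load at (actual) timepoint" i, with time in hours.

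Section 5.5.4.5 then fixes the data handling:

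- Below quantification: "Values below the LLOQ will be imputed with 1 when detected and with 0 when not detected".
- Missing first or last value: "missing at the first timepoint after infection and/ or the last timepoint after challenge, missing values should be imputed with 0".
- Everything else: "No other missing values will be imputed".
- Use: "These imputations will be used when calculating the AUC".

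The arms are compared with an exact Wilcoxon rank sum test and a geometric mean ratio (GMR) with a 95% confidence interval. AUC values are also summarised by arm and severity. Section 5.6.1.2 repeats the method for mild cases.

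**The concern.** The SAP describes no challenge. Infections are naturally acquired, and swabs start once a symptomatic episode has begun. There is thus no pre-infection sample for which 0 would be the natural value. In a PCR-confirmed episode a missing first swab means that the value is unknown, but the rule gives it the code that the preceding sentence of the rule reserves for not detected.

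Two things are at stake. First, the AUC of every affected participant is understated, so the descriptive means and medians are too low. Second, if first swabs go missing more often in one arm, the difference in missingness is read as a difference in viral load.

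Nothing else in the plan catches this. The planned sensitivity analysis varies the slope of a selection-bias model, not the handling of missing swabs. Section 5.5.3 defers local versus central PCR, saliva and LLOQ/LLOD handling to the Data Presentation Specifications, but not missing first samples. The viral-load endpoints in Section 5.6.1.1 do not do this: first viral load is the first value observed, and viral load over time borrows a value from an adjacent day.

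**Working it through.** The SAP gives no numerical result, sample size or missingness rate for VL-AUC, so there is no figure to reproduce. All viral-load curves, arm sizes and missing shares below are assumptions. The formula, the 48 h spacing and the imputation rule are the SAP's.

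**Scale of the imputed 0.** The ordinates are log10 viral load, and the log of 0 copies is undefined. The 0 can therefore only enter as 0 log10.

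**Algebra.** Let VL1 and VL2 be the true first two log10 values, at times t1 and t2. The first trapezoid is (VL1 + VL2)/2 × (t2 − t1). What is lost under each way of handling a missing VL1:

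- Set to 0 (SAP rule): VL1 × (t2 − t1)/2. The VL2 half of the trapezoid remains.
- Carry back VL2: (VL1 − VL2) × (t2 − t1)/2.
- Start at the first observed sample: (VL1 + VL2) × (t2 − t1)/2.

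**Example.** Assumed values 7, 6, 5, 4, 3, 2, 1, 0 log10 every 48 h:

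| Handling | Sum × 48 h | AUC (log10·h) | Change |
|---|---|---|---|
| Complete | (3.5 + 6 + 5 + 4 + 3 + 2 + 1) = 24.5 | 1176 | – |
| First value 0 | 24.5 − 3.5 = 21 | 1008 | −14.3% |
| Carry back 6 | 24.5 − 0.5 = 24 | 1152 | −2.0% |
| Start at second swab | 24.5 − 6.5 = 18 | 864 | −26.5% |

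**Range.** Assumed starts of 5 to 8 log10 and linear falls of 0.3 to 0.7 log10/day, floored at 0, over days 0 to 14:

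- Zero rule: loses 24 × VL1 = 120 to 192 log10·h. As a share, this runs from 192/1982.4 = 9.7% (start 8, fall 0.3) to 120/436.8 = 27.5% (start 5, fall 0.7).
- Carry-back: loses 0.7% to 7.7%.
- Starting at the first observed sample: loses 18.6% to 47.3%.

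These curves only decline. If viral load rises after the first swab, carry-back overstates by (VL2 − VL1) × 24, and the zero rule still understates by VL1 × 24. Carry-back stays closer unless VL2 exceeds twice VL1 on the log10 scale.

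**Between arms, no true effect.** If everyone follows the example curve, the null GMR is (1008/1176) raised to the difference in missing shares:

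- 30% versus 10% (vaccine versus placebo): 0.857^0.2 = 0.97
- 20% versus 10%: 0.857^0.1 = 0.985
- 10% versus 30%: 0.857^(−0.2) = 1.03
- Equal shares: 1.00

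A simulation gives the same picture. It assumed a mean start of 7 log10 with SD 1.2, arms of 50/100 and 100/200 cases, 1000 runs per setting and a two-sided 5% Wilcoxon test:

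| Missing first swabs, vaccine / placebo | Rule | GMR | Null rejection |
|---|---|---|---|
| 20% / 20% | 0 | about 1.00 | 3.8% to 5.1% |
| 30% / 10% | 0 | about 0.97 | 7.9% to 10.0% |
| 10% / 30% | 0 | about 1.03 | 7.6% to 9.0% |
| Either unequal split | carry back | 0.99 to 1.01 | 4.2% to 6.0% |

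**Last timepoint.** Section 5.2.2 defines resolution as two consecutive negative swabs plus two symptom-free days. A terminal 0 fits an episode that ended this way. It does not fit one whose last swab is missing while virus was still detected.

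**The case against.** The strongest reply is that the rule may seldom apply. The AUC uses actual dates and times, so a participant who reports late could simply have a later first timepoint and no missing value. The rule would then apply only to lost or failed samples, for which no arm difference has been argued. This stands in part: the SAP does not say whether the first timepoint is the scheduled episode start or the first swab obtained. It does not rescue the derivation, though. If the curve starts at the first swab obtained, the whole first interval is lost (864 in the example), which is worse than 1008.

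It is also fair to say that the endpoint is supportive, that the SAP already warns that the comparison may not be causal, and that other viral-load summaries are planned without a zero rule. These points limit the consequence but do not correct the derivation.

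A reader might infer more than the SAP supports:

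- *That the rule favours the vaccine.* Milder illness could delay or reduce first swabs in that arm, but the SAP gives no missingness rates and the bias can run either way.
- *That the near-peak part of the curve is deleted.* The rule shrinks the first trapezoid and does not remove it. The SAP does not say that the first swab is near peak.
- *That the rule was copied from a challenge study.* The wording suggests this, but the SAP does not state a source.
- *That the geometric mean fails because AUCs become 0.* Any other value above 0 keeps the AUC positive, since each is joined to a neighbour. An AUC of 0 needs every remaining value to be 0, which is an edge case.

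**Conclusion.** The rule is wrong as written for this endpoint. A missing first swab in a confirmed episode is scored as undetectable, and the affected AUC falls by VL1 × (t2 − t1)/2 whenever the true first value is above 0. That direction follows from the SAP's own formula. The size, about 10% to 28% per affected participant, rests on the assumed curves.

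Descriptive AUCs are biased downward by an amount that depends on how many first swabs are missing, which the SAP does not give. The arm comparison is biased only if that share differs between arms. Even at an assumed 30% versus 10%, the null GMR moves only to about 0.97 or 1.03, with null rejection of roughly 8% to 10% in place of 5%. VL-AUC is outside the confirmatory secondary endpoints of Section 5.5.2, so no confirmatory conclusion changes.

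**What to change.** In Section 5.5.4.5:

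1. Remove the challenge wording, and state that the imputed values are on the log10 scale.
2. Define the first timepoint (the scheduled start of the episode) so that it is clear when a value counts as missing.
3. Replace the zero at the first timepoint by carrying back the first observed value of the episode. Do not start the AUC at the first observed sample, because that loses more.
4. Use 0 at the last timepoint only where resolution is documented by two consecutive negative swabs, and state what is done for unresolved episodes. Ending the curve at the last observed sample is not neutral either: it also drops the half-trapezoid that a terminal 0 keeps.
5. Report the number of missing first swabs by arm, and add one sensitivity analysis that varies this rule.

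The same text then serves the mild-case analysis in Section 5.6.1.2. The cost is a few sentences of SAP wording, a small change to the derivation program and one additional table. No new data are needed.
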